## 11 EFFICACY ENDPOINTS

### 11.1 Primary Efficacy Endpoints

The primary endpoint for Part 1 is to evaluate the safety profile of escalating doses of continuous daily oral dosing of rucaparib and determine the MTD and RP2D. The recommended starting dose from Part 1 was established as 600 mg BID. The primary endpoint for Part 1 was based on safety review and analyses described in section 14.

The primary efficacy variable for Part 2A and Part 2B is the objective response rate (ORR) as assessed by RECIST v1.1. In addition, the primary endpoint will include an analysis including GCIG CA-125 response criteria.

The primary PK endpoints for Part 1 and Part 3 include a list of rucaparib PK parameters following continuous oral administration of rucaparib. PK analysis for oral rucaparib will be summarized in a separate PK report. This PK report includes details around the statistical analysis performed for these endpoints, hence no further detail around this endpoint will be included in this SAP.

### 11.2 Secondary Efficacy Endpoints

Secondary efficacy variables include:

- Characterize PK after a high-fat meal compared to the PK in a fasted state (Food effect) (Part 1 and Part 3 only). The PK analysis, including the analysis plan, will be included in the separate PK report as mentioned above, thus no further information around food effect will be included here.
- Evaluate the effects of oral rucaparib on  $Q_t/Q_{Tc}$  intervals by ECG (Part 1 only). A separate analysis plan and report based on this objective has been completed. Thus, no further info around this endpoint will be included here.
- Safety and tolerability as further detailed in section 14
- Duration of response in Ovarian Cancer patients (Part 2A and 2B only)
- Evaluate antitumor activity in various solid tumors (Objective Response in Part 1 and Part 3)
- Progression-Free Survival (PFS) in the Ovarian Cancer population (Part 2 only)
- Overall Survival (Part 2B only)

- ORR per RECIST v 1.1 and Gynecologic Cancer Intergroup (GCIG) CA-125 criteria in the Ovarian Cancer Population (Part 2 Only)

### 11.3 Exploratory Efficacy Variables

- To explore the relationship between the PK of oral rucaparib and the potential changes in QT/QTc interval (*Part 1 only*). A separate analysis plan and report is based on this objective and thus no further info around this endpoint will be included here.
- To profile circulating metabolites of oral rucaparib at steady state at the RP2D (*Part 1 only*). A separate analysis plan and report is based on this objective and thus no further info around this endpoint will be included here.
- To explore the association between genomic alterations identified in tumor tissue and clinical outcome (Parts 1, 2, and 3).
- Time to first response per RECIST v 1.1 in Part 2A and Part 2B
- Change from Baseline in Sum of the Longest Diameters (SLD) of Target Lesions for patients in Part 2A and Part 2B.

## 12 EFFICACY ANALYSIS

### 12.1 Primary Efficacy Analysis for Part 2A and Part 2B

The primary efficacy endpoint is defined as best confirmed response according to RECIST v1.1 as assessed by investigator as outlined below.

#### Confirmatory Response Rate by RECIST v1.1.

The confirmed response rate by RECIST v1.1 is defined as the proportion of patients with a confirmed CR or PR on subsequent tumor assessment at least 28 days after first occurrence of response. The ORR will be summarized with frequencies and proportion together with 95% Confidence Interval (CI) of the proportion using Clopper-Pearson methodology. In addition, the frequency and proportion of patients will be summarized for each of the confirmed response assessment in the following categories:

- Complete Response
- Partial Response
- Stable disease, including the following classifications
  - Patients with confirmed SD
  - CR/PR/SD followed by PD if the CR/PR/SD is at least 49 days from treatment start date.
  - Patients ongoing with a single response
  - Ongoing without a response
- Progressive Disease
- Not evaluable (e.g., discontinuations or deaths before first tumor assessment)

The primary efficacy endpoint was evaluated in the efficacy population in Part 2A and Part 2B of the study. In addition, the endpoint will also be summarized for the safety population (i.e., all treated patients).

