7.4.4 Treatment Beyond Progression

If the patient has met the criteria for radiologic progression by RECIST, but the patient is still receiving benefit from rucaparib (e.g., patient has mixed radiologic response or is continuing to have symptomatic benefit) according to the Investigator, then continuation of treatment will be considered. In such cases, the decision to continue will be made jointly between the Investigator and the Sponsor, and must be documented prior to continuing treatment with rucaparib. Patients will continue to have all protocol-required assessments specified in [Table 9](#), [Table 10](#), [Table 11](#), and [Table 13](#).

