CT scans are required within 7 days prior to the start of Cycles 3, 5, and 7, and then within 7 days prior to the start of every third cycle of treatment thereafter, beginning with Cycle 10. If an initial CR or PR is noted at Cycle 7 or beyond, confirmatory scans must be performed 4-6 weeks later. In the case of SD, follow-up measurements must have met the SD criteria at least once after study entry at a minimum interval of no less than 6–8 weeks.

Duration of Overall Response

The duration of overall response is measured from the time measurement criteria are met for CR or PR (whichever is first recorded) until the first date that recurrent or PD is objectively documented (taking as reference for PD the smallest measurements recorded since the treatment started).

The duration of overall CR is measured from the time measurement criteria are first met for CR until the first date that recurrent disease is objectively documented.

Duration of Stable Disease

SD is measured from the start of the treatment until the criteria for progression are met, taking as reference the smallest measurements recorded since the treatment started.

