#### Confirmatory Response Rate by RECIST v1.1 or GCIG CA-125 Criteria

The endpoint of ORR assessed by RECIST or GCIG CA-125 criteria is defined as a best confirmed response of CR or PR using RECIST v1.1 or a confirmed response per GCIG CA-125 criteria. The endpoint of CA-125 response rate is defined as a 50% reduction from baseline in CA-125 measurement as assessed by GCIG criteria and it is further described in Appendix A.

Only patients with elevated levels of CA-125 baseline value at least twice the upper limit of normal (>70 iU/mL) will qualify to have a response per GCIG CA-125 criteria.

The combined ORR will be assessed as indicated in Table 2.

Table 2: Overall Response by RECIST v1.1 and GCIG CA-125 Criteria Error! Reference source not found.		
RECIST Response	GCIG CA-125 Response	RECIST + GCIG CA-125 Combined
CR (requires normalization of CA-125)	CA-125 within normal range	Response
PR	Response	Response
PR	No Response	Response
SD	Response	Response
SD	No Response	No Response
PD	Response	No Response
PD	No Response	No Response

CR= Complete Response, PD = Progressive Disease, PR= Partial Response, SD = Stable Disease.

The response rate will be summarized with frequencies and percentages in addition to 95% Confidence Interval (CI) of the proportion using Clopper-Pearson methodology.

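### SAP 12.1 counts patients who are ongoing without a response as stable disease with no scan evidence or minimum time, and does not say that progression takes precedence

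*SAP*

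**What the plan says.** SAP section 12.1 sorts each Part 2A and Part 2B patient into complete response (CR), partial response (PR), SD, PD or NE. The SD category is introduced as "Stable disease, including the following classifications" and has four sub-classes:

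- confirmed SD
- "CR/PR/SD followed by PD if the CR/PR/SD is at least 49 days from treatment start date"
- ongoing with a single response
- "Ongoing without a response"

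The fourth carries no further condition. The NE category reads "Not evaluable (e.g., discontinuations or deaths before first tumor assessment"). The endpoint is summarized for the efficacy population and again for all treated patients. The response rate itself is "the proportion of patients with a confirmed CR or PR on subsequent tumor assessment at least 28 days after first occurrence of response".

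Protocol Appendix A is stricter on SD: "In the case of SD, follow-up measurements must have met the SD criteria at least once after study entry at a minimum interval", and it puts that interval at no less than 6–8 weeks. Its response grid gives NE when target lesions were not evaluated, non-target lesions have not progressed and there are no new lesions. It closes the best-response window at progression. Protocol 7.4.4 allows dosing to go on after progression by joint decision of investigator and sponsor: "If the patient has met the criteria for radiologic progression by RECIST, but the patient is still receiving benefit from rucaparib".

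For the combined endpoint, SAP 12.1 states: "The combined ORR will be assessed as indicated in Table 2". That table makes SD plus a CA-125 response a response, makes PD plus a CA-125 response a non-response, and has no NE row. The sentence defining the same endpoint accepts either a confirmed RECIST CR/PR or a confirmed CA-125 response, without reference to the RECIST class.

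**The concern.** A best-response category should follow from tumor measurements. The fourth SD sub-class follows from two other facts: the patient is still on treatment, and no CR or PR has been recorded. A patient whose scans say nothing can be reported as stable simply for being on drug at the data cut.

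Two outputs are exposed. In the response table, SD would be overstated at the expense of NE, and possibly of PD. In the combined RECIST/CA-125 analysis, which SAP 11.1 attaches to the primary endpoint and SAP 11.2 lists again as secondary, Table 2 makes the RECIST class decide whether a CA-125 response counts. Any bias runs toward more SD and more combined responders.

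**Working it through.** **1. The plan's own figures.** SAP 3.2.1.3 gives exact (Clopper-Pearson) 95% intervals at n=40, the method 12.1 also uses. Recomputed: 12/40 gives 16.6–46.5, 16/40 gives 24.9–56.7, and 20/40 gives 33.8–66.2. These match the stated 17–47, 25–57 and 34–66. No stated figure is in dispute; the point is one of definition.

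**2. What the fourth sub-class adds.** The first three SD sub-classes each rest on a tumor reading. Ongoing patients with confirmed SD are already in the first, and ongoing patients with one unconfirmed response are in the third. The fourth therefore adds only ongoing patients without confirmed SD. A single unconfirmed SD scan was probably intended, but the wording does not say so.

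**3. Four ongoing patients, side by side.**

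| Patient still on drug, no CR/PR | SAP 12.1, read literally | Protocol Appendix A |
|---|---|---|
| No post-baseline scan | SD | SD requirement not met |
| Target lesions never evaluated, no sign of PD elsewhere | SD | NE |
| One SD reading, at the first scheduled scan | SD | SD interval generally not reached (step 4) |
| First reading PD, dosing continued under 7.4.4 | Fits both PD and the ongoing sub-class; no order stated | PD |

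**4. Timing of the first scan.** With 21-day cycles and no delay, Cycle 3 starts on Day 2 × 21 + 1 = 43. The scan is due in the 7 days before, so on Days 36–42. An SD reading then, followed by PD, fails the SAP's 49-day condition. The same reading in a patient still on drug is SD with no time condition. Appendix A's 6–8 weeks is 42–56 days, so a Day 36–42 scan generally falls short of that too.

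**5. Which population.** SAP section 5 admits a patient to the efficacy population only with at least one post-baseline disease assessment, but does not say that it must be evaluable. Patients with no scan therefore appear only in the all-treated summary. Patients whose every assessment was unevaluable can appear in both.

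**6. Size per patient.**

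- Confirmed RECIST response rate: change of 0, because SD is never a response.
- SD, NE or PD share: 1/41 = 2.4 points, or 1/40 = 2.5 points.
- Combined rate, if Table 2 governs and the patient is a CA-125 responder: the same 2.4–2.5 points.

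The number affected is not in the documents. As an illustration only, take 29/40 = 72.5%, the count nearest the 73% that SAP 3.2.1.3 reports for an earlier group, and assume that 0 to 4 such patients become non-responders:

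| Assumed number reclassified | Combined rate | Exact 95% CI |
|---|---|---|
| 0 | 29/40 = 72.5% | 56.1–85.4 |
| 1 | 28/40 = 70.0% | 53.5–83.4 |
| 2 | 27/40 = 67.5% | 50.9–81.4 |
| 4 | 25/40 = 62.5% | 45.8–77.3 |

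The range 0–4 is an assumption without a source, and the true number may be zero.

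**The case against.** The best defense is that the two ongoing sub-classes are shorthand for patients without progression whose confirmation is still pending. The NE list gives examples and is not exhaustive, and Appendix A already assigns NE when target lesions are not evaluated. Patients with no scan are outside the efficacy population. In Part 2A such patients should be close to absent: enrollment ended in April 2015, and the SAP cites a June 2016 amendment, so anyone still on drug would be many scheduled scans past baseline.

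Most of this stands as a limit on size. It does not remove the defect, because the SAP places the ongoing sub-class under SD without condition, while its NE examples name only patients who discontinued or died.

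A reader might also draw three stronger conclusions that the documents do not support.

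- *Patients dosed beyond progression count as SD.* PD is its own category in the same list, Appendix A ends best response at progression, and SAP 12.2.2 uses the first progression date, though only for duration of response. PD is the natural class. What is missing is a sentence stating the order.
- *The SD label alone creates combined responders.* The text definition of that endpoint already counts a confirmed CA-125 response whatever the RECIST class, and Table 2 is silent on NE. The label matters only if Table 2 governs. The text and the PD rows of Table 2 contradict each other, which is a separate ambiguity to resolve.
- *The problem is common.* The gaps between RECIST and combined rates (15 versus 17 of 20 in Part 2A; 47% versus 73% in the group with three or more prior regimens) show that CA-125 responses add responders. They do not show that anyone was unevaluable or misclassified.

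**Conclusion.** The concern holds in limited form. SAP 12.1 defines one SD sub-class by treatment status, in conflict with protocol Appendix A. Read literally, it moves ongoing patients with no evaluable scan from NE to SD. The missing precedence of PD over ongoing status is a gap in the text rather than a rule that turns progressors into SD.

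The confirmed RECIST response rate does not change. The SD, NE and possibly PD shares can be off by 2.4–2.5 points per patient, mainly in the all-treated summary. The combined rate can move by the same amount only if Table 2 governs and the patient has a CA-125 response. How many patients are affected depends on data maturity at the cut-off, which the documents do not give. The CA-125 response details are in a SAP appendix that is not in the supplied text.

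**What to change.** Make four changes in SAP 12.1:

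1. Replace the sub-class with: ongoing, no CR/PR, no PD, and at least one evaluable post-baseline assessment of SD at least X days from treatment start. Use one X that reconciles the SAP's 49 days with Appendix A's 6–8 weeks. State that ongoing patients not yet meeting it, including those with only an earlier SD scan, are NE.
2. State that PD before a CR/PR or qualifying SD is classed PD even if treatment continues under protocol 7.4.4.
3. State that ongoing patients with no evaluable post-baseline assessment are NE.
4. Add NE rows to Table 2, and reconcile the table with the either/or definition in the same section, which conflicts with its PD rows.

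The cost is a few sentences and a programming change, with no new data. The SD share, and possibly the combined rate, becomes slightly lower. If X were 49, an ongoing patient with only the first scheduled scan would stay NE until the scan before Cycle 5. That cycle starts on Day 4 × 21 + 1 = 85, so the scan falls on about Days 78–84.

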
Introduction and Study Overview (cont)	
 Part 3 (Phase II PK portion) = Further evaluation of PK of higher dose strength tablets at the RP2D in patients with any advanced solid tumor, inclusive of lymphoma, with evidence of a BRCA mutation (germline or somatic) 	
Planned Number of Patients	
Number of patients:
 
 Part 1: approximately 50 – 60 patients Part 2: up to 41 evaluable patients in Part 2A and 40 evaluable patients in Part 2B Part 3: approximately 20 evaluable patients 
Patients will enroll in to either Part 1, Part 2, or Part 3 of the study, not in to multiple parts.
	
Planned Number of Sites	
This is a multicenter, multinational study. Patients will be enrolled from approximately 4 – 6 sites in Part 1, approximately 20 sites in Part 2, and approximately 8 sites in Part 3.
	
Study Objectives and Endpoints	
Primary, secondary, and exploratory objectives and endpoints are shown below.
	
	Primary Objectives	Primary Endpoints
	
To evaluate the safety profile of escalating doses of continuous daily oral rucaparib in patients with advanced solid tumors, and to determine the MTD and RP2D (Part 1 only)
	
The incidence of Grade 3 or 4 adverse events (AEs) and clinical laboratory abnormalities defined as dose-limiting toxicities (DLTs)

	
To characterize the pharmacokinetic (PK) profile of oral rucaparib when administered as a continuous daily dose (Part 1 and Part 3 only)
	
PK parameters: area under the curve from time zero to the time with the last measurable concentration (AUC_{0-t}), AUC from time zero to infinity ($AUC_{0-\infty}$), maximum concentration (C_{max}), time to maximum concentration (T_{max}), elimination half-life ($t_{1/2}$), elimination rate constant (k_{el}), apparent volume of distribution at steady state after nonintravenous administration (V_{ss}/F), and apparent total plasma clearance (Cl/F)

To evaluate overall response rate (ORR) in patients with relapsed, high-grade serous or endometrioid epithelial ovarian, fallopian tube, or primary peritoneal cancer associated with a BRCA mutation (Part 2 only) [henceforth abbreviated to ovarian cancer (OC) population]
	
ORR per Response Evaluation Criteria in Solid Tumors (RECIST) Version 1.1; secondary analysis including Gynecologic Cancer InterGroup (GCIg) cancer antigen-125 (CA-125) criteria
	

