6.2 Inclusion Criteria

All patients enrolling into **Part 1 (Phase I portion), Part 2 or Part 3 (Phase II portions)** must meet all of the following inclusion criteria:

1. Understand and voluntarily sign an Institutional Review Board/Independent Ethics Committee-approved informed consent form prior to any study-specific evaluation
2. Be ≥ 18 years of age at the time the informed consent form is signed
3. Have Eastern Cooperative Oncology Group (ECOG) performance status of 0 to 1
4. Have a life expectancy of at least 3 months
5. Have adequate organ function, confirmed by the following laboratory values obtained ≤ 14 days prior to the first dose of rucaparib:

Bone Marrow Function

- Absolute neutrophil count (ANC) $\geq 1.5 \times 10^9/L$
- Platelets $> 100 \times 10^9/L$
- Hemoglobin ≥ 9 g/dL

Hepatic Function

- Aspartate aminotransferase (AST) and ALT $\leq 3 \times$ upper limit of normal (ULN); if liver metastases, then $\leq 5 \times$ ULN
- Bilirubin $\leq 1.5 \times$ ULN ($< 2 \times$ ULN if hyperbilirubinemia is due to Gilbert's syndrome)
- Serum albumin ≥ 30 g/L (3.0 g/dL) (**Part 2B only**)

Renal Function

- Serum creatinine $\leq 1.5 \times$ ULN

Patients enrolling into **Part 1 (Phase I portion)** must also meet the following inclusion criteria:

6. (a) Have a histologically or cytologically confirmed solid tumor (lymphoma is included in this category) that is locally recurrent or metastatic and has progressed on standard treatment.
7. (a) Have left ventricular ejection fraction (LVEF) $>$ lower level of normal (LLN) as determined by echocardiogram (ECHO) or multigated acquisition (MUGA) scan evaluation using local institutional standard
8. (a) Be willing and able to eat a high-fat breakfast on Day 1 of the study (**Note: only applicable for patients being screened for enrollment into a food-effect PK cohort**)
9. (a) Have a deleterious *gBRCA* mutation (**Note: only applicable for patients being screened for enrollment into the RP2D Expansion cohort**)

All patients enrolling into **Part 2 (Phase II portion in OC patients)** must also meet the following inclusion criteria:

6. (d) Have a known deleterious *BRCA* mutation (germline or somatic), as determined by a local laboratory that has received an international or country-specific quality standards certification
7. (d) Have evidence of measurable disease as defined by RECIST v1.1

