9.10.5 Efficacy Evaluations

9.10.5.1 Tumor Assessments

For Part 1 and Part 2, tumor assessments will be performed at screening, within 7 days prior to the start of Cycles 3, 5, and 7, within 7 days prior to the start of every three cycles thereafter, beginning with Cycle 10, and at the end-of-treatment visit.

For Part 2B, tumor assessments will also be performed during the long-term follow-up period for any patient who discontinued from study treatment for reason other than disease progression or death, within 7 days prior to the start of every 9 weeks until radiologically confirmed disease progression, death, or initiation of subsequent treatment. Patients who have been on study at least 18 months may decrease the frequency of tumor scans to every 16 weeks (± 14 days).

For Part 3, tumor scans will be performed at screening, within 7 days prior to the start of Cycles 3, 5, and 7, and within 7 days prior to the start of every three cycles thereafter, beginning with Cycle 10.

If initial CR or PR is noted at Cycle 7 or beyond, confirmatory scans must be performed 4–6 weeks later. Tumor response will be interpreted using RECIST Version 1.1 ([Appendix A](#)).

Tumor assessments should consist of clinical examination and appropriate imaging techniques (preferably CT scans of the chest, abdomen, and pelvis with appropriate slice thickness per RECIST); other studies (MRI, X-ray, PET, and ultrasound) may be performed if required. The same methods used to detect lesions at baseline are to be used to follow the same lesions throughout the clinical study. Investigators should perform scans of the anatomical sites that, in their judgment, are appropriate to assess based on each patient's tumor status. For patients in Part 2 and Part 3, tumor scans will be collected for possible evaluation by independent radiology review.

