11.2.4.1 Overall Response Rate - Primary Endpoint (Part 2)

A primary efficacy endpoint in Part 2 of the study (ORR) is the best overall response recorded from the start of the treatment until disease progression or recurrence. The ORR will be summarized for the tumor-evaluable population enrolled in Part 2 with frequencies and percentages.

11.2.4.2 Secondary Analyses and Endpoints in Part 2 and 3

11.2.4.2.1 ORR per RECIST v 1.1 and Gynecologic Cancer Intergroup (GCIG) CA-125 Criteria (Part 2)

The proportion of patients with the best response by RECIST v 1.1²⁷ of ‘Complete Response’ or ‘Partial Response’ or response according to the GCIG CA-125^{28,29} criteria will be summarized with number of patients and percent and for each response category.

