## 5 ANALYSIS POPULATIONS

**PK-Evaluable Population (Part 1 and Part 3 only)**—all patients who have received at least one dose of rucaparib and have had adequate PK samples available for determination of the PK profile. Adequacy will be determined on a case-by-case basis and will be assessed prior to analysis of the blood samples.

**Food-Effect PK Population (Part 1 and Part 3 only)**—all patients enrolled as part of the food-effect in Part 1 or Part 3 of the study and who received rucaparib on both Day -7 and Day 1 (Cycle 1), complied with the fed and fasted requirements, and have sufficient PK data for a comparison to be made between the fasted and fed state.

**ECG-Evaluable Population (Part 1 only)**—all patients who have received at least one dose of rucaparib and had adequate PK and ECG assessments performed for determination of the ECG effects in relationship to the PK of rucaparib.

**Safety Population**—all patients who have received at least one dose of rucaparib.

**DLT-Evaluable Population (Part 1 only)**—all patients enrolled into Part 1 of the study who received at least 17 complete days of rucaparib and completed Cycle 1 of treatment, or who experienced a DLT in Cycle 1.

**Efficacy Population**—all patients who met eligibility criteria, received at least one dose of rucaparib, have measurable tumor lesions at baseline, and have at least one post-baseline disease assessment.

Separate PK and ECG reports will be included as appendices to the clinical study report, hence only the Safety population, DLT-Evaluable Population and Efficacy population will be summarized for the statistical output in the body of the report.

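### The primary response rate in Parts 2A and 2B leaves out treated patients who were never assessed; the all-treated rate, already planned, should lead

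*SAP*

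**What the plan says.** SAP 12.1 sets the analysis population for the confirmed RECIST response rate: "The primary efficacy endpoint was evaluated in the efficacy population in Part 2A and Part 2B of the study". SAP section 5 restricts that population to eligible, dosed patients who "have measurable tumor lesions at baseline, and have at least one post-baseline disease assessment". Protocol 11.1 sets the same conditions under the name Efficacy-Evaluable Population.

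SAP 12.1 then adds a second summary: "In addition, the endpoint will also be summarized for the safety population (i.e., all treated patients". Its list of response categories includes "Not evaluable (e.g., discontinuations or deaths before first tumor assessment".

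Protocol 11.2.4.1 uses another name: "The ORR will be summarized for the tumor-evaluable population enrolled in Part 2 with frequencies and percentages". Protocol 11.1 defines no population of that name.

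Two provisions limit how many patients can be affected. Protocol 9.10.5.1 schedules scans before Cycles 3, 5 and 7, then every three cycles "beginning with Cycle 10, and at the end-of-treatment visit", so a patient who stops early is still due a scan. Protocol 6.2 requires of every Part 2 patient: "Have evidence of measurable disease as defined by RECIST v1.1".

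The protocol synopsis states the Part 2 sample size as "up to 41 evaluable patients in Part 2A and 40 evaluable patients in Part 2B", while Protocol 11.4.1 describes the Simon stages in terms of patients treated. Protocol 11.2.2 and SAP section 6 plan counts of population allocation, and SAP section 7 plans a listing of major deviations.

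**The concern.** Membership of the primary population depends on something that happens after treatment starts. The first scheduled on-treatment scan is due before Cycle 3, about 6 weeks in (2 × 21 days). A treated patient with no post-baseline assessment cannot meet SAP 12.1's definition, which needs a response and its confirmation at least 28 days later. Dropping such patients removes only non-responders.

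Part 2 has no control arm in which the same omission would occur. Part 2A is judged against fixed rates of 5% and 20%, and Part 2B is read against 20%. An upward shift therefore goes straight into the comparison. The documents give no reason for putting the efficacy population ahead of all treated patients.

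**Working it through.** **Plan's own figures.** Part 2A: continue if X1 ≥ 2 of 21, succeed if X1 + X2 ≥ 5 of 41, with X1 ~ Bin(21, p) and X2 ~ Bin(20, p). The exact P(X1 ≥ 2 and X1 + X2 ≥ 5) is 0.0457 at p = 0.05 and 0.9017 at p = 0.20, in line with the stated 5% and 90%. Part 2B: the Clopper-Pearson 95% limits are the 0.025 quantile of Beta(x, n − x + 1) and the 0.975 quantile of Beta(x + 1, n − x). They give 12/40: 16.6–46.5; 16/40: 24.9–56.7; 20/40: 33.8–66.2. All three match the plan's table after rounding.

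**Inputs not in the documents.** No count of unassessed patients is given. I assume a share q of treated patients between 3% and 15%. The lower end is close to the only related figure in the documents, five deaths among 163 patients (Protocol 3.2.2.1, Safety): 5/163 = 3.1%. That figure counts deaths at any time on study or within 30 days of last dose, and does not cover withdrawals or missed scans. The upper end has no source in the documents; it only shows the range.

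**Effect on the rate.** With r responders, N treated and k unassessed, the efficacy-population rate is r/(N − k) and the all-treated rate is r/N. The ratio is N/(N − k) = 1/(1 − q): 1/0.97 = 1.03 and 1/0.85 = 1.18.

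**Effect on the Part 2B lower limit, read against 20%.**

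| Efficacy population | Lower limit | All treated | Lower limit | Unassessed | Reading changes? |
|---|---|---|---|---|---|
| 13/37 | 20.2% | 13/40 | 18.6% | 3/40 = 7.5% | yes |
| 14/40 | 20.6% | 14/41 | 20.1% | 1/41 = 2.4% | no |
| 14/40 | 20.6% | 14/42 | 19.6% | 2/42 = 4.8% | yes |
| 15/40 | 22.7% | 15/46 | 19.5% | 6/46 = 13.0% | yes |
| 16/40 (plan's 40% case) | 24.9% | 16/47 | 20.9% | 7/47 = 14.9% | no |
| 19/40 (near the cited 47%) | 31.5% | 19/47 | 26.4% | 7/47 = 14.9% | no |

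**Part 2A decision.** Protocol 3.2.2.1 (Efficacy) already reports 15 partial responses among 20 patients, against a requirement of 5 among 41. Adding non-responders to the denominator does not alter that count.

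**Moving the Simon rule as well.** Suppose the 5-of-41 rule were applied to 41 treated patients, with a 20% rate among those assessed. The effective rate is then 0.20 × (1 − q). Power falls from 90.2% to 87.6%, 84.4% and 80.6% at q = 5%, 10% and 15%.

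**Resulting N.** If enrolment runs to 41 and 40 evaluable, treated N = evaluable/(1 − q). At q = 3.1% and 15%, 41 gives 42.3 and 48.2, and 40 gives 41.3 and 47.1.

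**The case against.** The strongest reply is that nothing is hidden. The all-treated rate is already planned, and the population counts show how many patients were left out. The current choice also matches sample sizes stated in evaluable patients. Few patients should be affected: entry needs ECOG 0–1 and a life expectancy of at least 3 months, and an end-of-treatment scan is due. Part 2B has no formal decision rule, and the plan claims an interval above 20% only for an observed rate of 40% or more; every changed reading in the table lies below that. SAP 12.1 is also written in the past tense, so changing the order now would follow open-label data, and it would bring back ineligible patients, whose effect can go either way.

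Most of this stands, and it limits the size of the point. It does not remove it: of two planned rates, the one put first is the one that missing assessments can only raise.

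A reader might infer more in three ways.

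- **Inflated type I error in Part 2A.** Reading the 5% null as an all-treated rate gives an evaluable rate of 0.05/(1 − q) and an error of 5.1–8.0% for q of 3.1–15%. The documents do not say that the null is an all-treated rate. The 4.6% holds for the population to which the rule is applied, and relabelling the denominator would not change the number of responders.
- **A redundant Not evaluable category in the primary population.** The SAP's wording gives examples only. Protocol Appendix A also assigns not evaluable when target lesions were not evaluated, so an assessed patient can still fall there.
- **A Part 2A conclusion at risk.** The response counts already reported rule this out.

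**Conclusion.** The point holds as a cheap improvement. The lead estimate in a single-arm comparison excludes treated patients who cannot be confirmed responders, and the bias from that exclusion runs in one direction. The effect is probably small, and it is nil if every treated patient was assessed. That may be so in Part 2A, where 41 appears both as the number enrolled (Protocol 5.1.3) and as the number evaluable (Protocol 11.4.1).

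Over the assumed 3–15%, neither the Part 2A decision nor the plan's 40% case in Part 2B changes. What can change is the reading of a Part 2B result of roughly 32–38% against 20%, and for 14 responders two unassessed patients are enough. These figures count unassessed patients as non-responders and leave aside exclusions for ineligibility, which have no fixed direction.

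**What to change.** - In SAP 12.1, make the safety-population (all treated) response rate and its Clopper-Pearson interval the lead estimate in Parts 2A and 2B. Count patients with no post-baseline assessment as non-responders under Not evaluable. Keep the efficacy-population rate as supportive.
- Show beside the rate how many treated patients the efficacy population excludes, by reason: no assessment, ineligible, no measurable lesion. The planned disposition counts and deviation listing supply most of this.
- Leave the Part 2A Simon rule (2 of 21, 5 of 41) and the sample sizes tied to evaluable patients, and say so explicitly, so that the 4.6% error and 90.2% power still apply.
- In Protocol 11.2.4.1, replace the undefined population name with a defined one.
- If the analysis has already been run, state that the order of presentation was changed.

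The cost is wording and one small table, with no new data. The stated rate may be slightly lower. The all-treated N may differ from 41 and 40 (about 42–48 and 41–47 over the assumed range), so the n = 40 interval table becomes approximate for the lead estimate. Ineligible treated patients return to the denominator.
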